## CONFIDENTIAL

116938 (FLU Q-PAN H5N1=AS03-023)  
Protocol Amendment 2 Final

Treatment name	Vaccine /product name	Formulation	Presentation	Vial Volume*	Final Dose: Volume per product (mL)**	No. doses per subject	Final Dose: Total Volume (mL)***
3.75 mcg H5N1 HA + AS03D	FLU-Q-PAN	A/Indonesia/05/2005(H5N1)=3.75µg (30 µg/mL vial)	translucent to whitish suspension	3.1 ml	0.125 ml	2	0.25 ml
	AS03C	Emulsion containing tocopherol, tocopherol=2.97mg per 0.25 mL dose Final vaccine dose = emulsion containing tocopherol, tocopherol = 1.48 mg)	whitish to yellowish homogenous milky liquid emulsion	3.1 ml	0.125 ml		
3.75 mcg H5N1 HA	FLU-Q-PAN	A/Indonesia/05/2005=3.75µg (15 µg/mL vial)	translucent to whitish suspension	3.1 ml	0.25 ml	1	0.25 ml

\*for adjuvanted vaccines, full vials of antigen and adjuvant are mixed.; \*\* The volume of each component (antigen, adjuvant) administered in a final vaccine dose \*\*\*Total target volume of the antigen/adjuvant mixture to be administered to the subject. Syringes may only be calibrated to two decimal places.

## **6.2. Storage and handling of study vaccine**

The study vaccine components must be stored at the respective label storage temperature conditions in a safe and locked place. Access to the storage space should be limited to authorized study personnel. The storage conditions will be assessed during pre-study activities under the responsibility of the sponsor study contact. The storage temperature should be continuously monitored with calibrated (if not validated) temperature monitoring device(s) and recorded. Refer to the Module on Clinical Trial Supplies in the SPM for more details on storage of the study vaccine(s)/product(s).

Temperature excursions must be reported in degrees Celsius.

Any temperature excursion outside the range of 0.0 to +8.0°C (for +2 to +8°C/+36 to +46°F label storage condition) impacting investigational medicinal products (IMPs) must be reported in the appropriate (electronic) temperature excursion decision form ([e]TDF). The impacted IMPs must not be used and must be stored in quarantine at label temperature conditions until usage approval has been obtained from the sponsor.

In case of temperature excursion below +2.0°C down to 0.0°C impacting IMP(s) there is no need to report in (e)TDF, but adequate actions must be taken to restore the +2 to +8°C/+36 to +46°F label storage temperature conditions. The impacted IMP(s) may still be administered, but the site should avoid re-occurrence of such temperature excursion. Refer to the Module on Clinical Trial Supplies in the SPM for more details on actions to take.

Refer to the Module on Clinical Trial Supplies in the SPM for details and instructions on the temperature excursion reporting and usage decision process, packaging and accountability of the study vaccine components.

### 6.3. Dosage and administration of study vaccine(s)/product(s)

**Table 13 Dosage and administration**

Type of contact and timepoint	Dose	Study Group	Vaccine/Product		Route 	Site	Side
			Antigen	Adjuvant vial*			
Visit 1 Day 0 )	1	190_B	FLU-Q-PAN	AS03A	IM	Anterolateral thigh	Left
Visit 2 (Day 21 )	2	190_B		AS03A			Right
Visit 6 (Day 385)	3	190_B		None			
Visit 1 Day 0 )	1	090_C	FLU-Q-PAN	AS03A	IM	Anterolateral thigh	Left
Visit 2 (Day 21 )	2	090_C		AS03A			Right
Visit 6 (Day 385)	3	090_C		None			
Visit 1 Day 0 )	1	190_C	FLU-Q-PAN	AS03B	IM	Anterolateral thigh	Left
Visit 2 (Day 21 )	2	190_C		AS03B			Right
Visit 6 (Day 385)	3	190_C		None			
Visit 1 Day 0 )	1	375_C	FLU-Q-PAN	AS03B	IM	Anterolateral thigh	Left
Visit 2 (Day 21 )	2	375_C		AS03B			Right
Visit 6 (Day 385)	3	375_C		None			
Visit 1 Day 0 )	1	375_D	FLU-Q-PAN	AS03C	IM	Anterolateral thigh	Left
Visit 2 (Day 21 )	2	375_D		AS03C			Right
Visit 6 (Day 385)	3	375_D		None			

Intramuscular (IM); \*adjuvant vial to be used

### 6.4. Replacement of unusable vaccine/product doses

In addition to the vaccine/product doses provided for the planned number of subjects (including over-randomisation when applicable), at least 10% additional vaccine/product doses will be supplied to replace those that are unusable.

The investigator will use SBIR to obtain the replacement vial number. The replacement numbers will be allocated by kit/dose/component. The system will ensure, in a blinded manner, that the replacement vial matches the formulation the subject was assigned to by randomisation.

### 6.5. Contraindications to subsequent vaccination

The following events constitute absolute contraindications to further administration of Q-Pan H5N1 vaccine. If any of these events occur during the study, the subject must not receive additional doses of vaccine but may continue other study procedures at the discretion of the investigator (Section 9).

- Anaphylaxis following study vaccine administration.
- Any condition that in the judgment of the investigator would make intramuscular injection unsafe, or discovery of a change in the subject's status which renders his/her parent(s)/LAR(s) unable to comply with protocol-mandated safety follow-up.

The following events constitute contraindications to administration of Q-Pan H5N1 vaccine at that point in time; if any of these events occur at the time scheduled for vaccination, the subject may be vaccinated at a later date, within the time window

specified in the protocol (Section 5.5), or the subject may be withdrawn at the discretion of the investigator (Section 9).

- Acute disease and/or fever at the time of vaccination.
  - Fever is defined as temperature  $\geq 38.0^{\circ}\text{C}/100.4^{\circ}\text{F}$  by any route (axillary assessment preferred).
  - Subjects with a minor illness (such as mild diarrhoea, mild upper respiratory infection) without fever can be administered all vaccines/products.

## **6.6. Warnings and precautions**

Refer to the approved product label/package insert.

## **6.7. Concomitant medications/products and concomitant vaccinations**

At each study visit/contact, the investigator should question the subject and/or the subject's parent(s)/LAR(s) about any medications/products taken and vaccinations received by the subject.

### **6.7.1. Recording of concomitant medications/products and concomitant vaccinations**

The following concomitant medication(s)/product(s)/vaccine(s) must be recorded in the eCRF.

- All concomitant medications /products except vitamins and dietary supplements, administered in the period starting 30 days before the first dose of study vaccine and continuing for at least 21 days after each priming dose and for 30 days after the booster (Day 0 to Day 21; Day 21 to Day 42; Day 385 to Day 415).
- Any prophylactic medication (i.e. medication administered in the absence of ANY symptom and in anticipation of a reaction to the vaccination).
- Any antipyretics administered in the period starting 6 hours before vaccination and ending 12 hours after vaccination (there is a specific eCRF page where this information is captured).
- Any concomitant medications/products/vaccines listed in Section 6.7.2.
- Any concomitant medications/products/vaccines administered during the study period for the treatment of a SAE /pIMD, or relevant to a SAE/pIMD that is to be reported as per protocol. In addition, concomitant medications relevant to SAEs and pIMDs need to be recorded on the expedited Adverse Event report.

**6.7.2. Concomitant medications/products/vaccines that may lead to the elimination of a subject from ATP analyses**

The use of the following concomitant medications/products/vaccines will not require withdrawal of the subject from the study but may determine a subject's evaluability in the ATP analysis. See Section [10.4](#) for cohorts to be analysed.

- A vaccine not foreseen by the study protocol administered in the period starting 30 days before the first dose of study vaccine through Day 42 visit (Day -30 to Day 42 visit); and for the booster, administration of an inactive vaccine within 14 days or of a live attenuated vaccine within 30 days before through 30 days after the booster vaccination (note: routine vaccinations may be administered on Day 42 visit only after all study assessments are made).
- Any investigational or non-registered product (drug or vaccine) other than the study vaccine used during the study period.
- Immunosuppressants or other immune-modifying drugs administered chronically (i.e. for 14 or more days) during the entire study period. For corticosteroids, this will mean a dose of prednisone or equivalent of  $> 2 \text{ mg/kg/day}$  of body weight (for persons who weigh  $< 10 \text{ kg}$ ), or  $\geq 20 \text{ mg/day}$  (for persons who weigh  $\geq 10 \text{ kg}$ ). Inhaled and topical steroids are allowed.
- Long-acting immune-modifying drugs administered at any time during the study period (e.g. infliximab).
- Immunoglobulins or any blood products for 3 months before any protocol-mandated blood sampling.

A detailed, comprehensive list of reasons for elimination from ATP analyses will be established at the time of data cleaning.

In case an emergency mass vaccination for an unforeseen public health threat (e.g.: a pandemic) is organised by the public health authorities, outside the routine immunisation program, the time period described above can be reduced if necessary for that vaccine provided it is licensed and used according to its Prescribing Information and according to the local governmental recommendations and provided a written approval of the Sponsor is obtained.

**6.8. Intercurrent medical conditions that may lead to elimination of a subject from ATP analyses**

At each study visit subsequent to the first vaccination, it must be verified if the subject has experienced or is experiencing any intercurrent medical condition. If it is the case, the condition(s) must be recorded in the eCRF.

**7. HEALTH ECONOMICS**

Not applicable.

## 8. SAFETY

The investigator or site staff is/are responsible for the detection, documentation and reporting of events meeting the criteria and definition of an adverse event (AE) or serious adverse event (SAE) as provided in this protocol.

Each subject's parent(s)/LAR(s) will be instructed to contact the investigator immediately should the subject manifest any signs or symptoms they perceive as serious.

### 8.1. Safety definitions

#### 8.1.1. Definition of an adverse event

An AE is any untoward medical occurrence in a clinical investigation subject, temporally associated with the use of a medicinal product, whether or not considered related to the medicinal product.

An AE can therefore be any unfavourable and unintended sign (including an abnormal laboratory finding), symptom, or disease (new or exacerbated) temporally associated with the use of a medicinal product. For marketed medicinal products, this also includes failure to produce expected benefits (i.e. lack of efficacy), abuse or misuse.

Examples of an AE include:

- Exacerbation of a chronic or intermittent pre-existing condition including either an increase in frequency and/or intensity of the condition.
- New conditions detected or diagnosed after investigational vaccine administration even though they may have been present before the start of the study.
- Signs, symptoms, or the clinical sequelae of a suspected overdose of either the investigational vaccine or a concurrent medication (overdose per se should not be reported as an AE/SAE).
- Signs and/or symptoms temporally associated with vaccine administration.
- Pre- or post-treatment events that occur as a result of protocol-mandated procedures (i.e. invasive procedures, modification of subject's previous therapeutic regimen).

AEs to be recorded as endpoints (solicited AEs) are described in Section 8.1.3. All other AEs will be recorded as UNSOLICITED AEs.

Examples of an AE DO NOT include:

- Medical or surgical procedures (e.g. endoscopy, appendectomy); the condition that leads to the procedure is an AE/SAE.
- Situations where an untoward medical occurrence did not occur (e.g. social and/or convenience admission to a hospital, admission for routine examination).
- Anticipated day-to-day fluctuations of pre-existing disease(s) or condition(s) present or detected at the start of the study that do not worsen.

- Pre-existing conditions or signs and/or symptoms present in a subject prior to the first vaccination. These events will be recorded in the medical history section of the eCRF.

### **8.1.2. Definition of a serious adverse event**

**A SAE is any untoward medical occurrence that:**

- a. Results in death,
- b. Is life-threatening,

Note: The term 'life-threatening' in the definition of 'serious' refers to an event in which the subject was at risk of death at the time of the event. It does not refer to an event, which hypothetically might have caused death, had it been more severe.

- c. Requires hospitalisation or prolongation of existing hospitalisation,

Note: In general, hospitalisation signifies that the subject has been admitted at the hospital or emergency ward for observation and/or treatment that would not have been appropriate in the physician's office or in an out-patient setting. Complications that occur during hospitalisation are also considered AEs. If a complication prolongs hospitalisation or fulfils any other serious criteria, the event will also be considered serious. When in doubt as to whether 'hospitalisation' occurred or was necessary, the AE should be considered serious.

Hospitalisation for elective treatment of a pre-existing condition (known or diagnosed prior to informed consent signature) that did not worsen from baseline is NOT considered an AE.

- d. Results in disability/incapacity, OR

Note: The term disability means a substantial disruption of a person's ability to conduct normal life functions. This definition is not intended to include experiences of relatively minor medical significance such as uncomplicated headache, nausea, vomiting, diarrhoea, influenza like illness, and accidental trauma (e.g. sprained ankle) which may interfere or prevent everyday life functions but do not constitute a substantial disruption.

- e. Is a congenital anomaly/birth defect in the offspring of a study subject.

Medical or scientific judgement should be exercised in deciding whether reporting is appropriate in other situations, such as important medical events that may not be immediately life-threatening or result in death or hospitalisation but may jeopardise the subject or may require medical or surgical intervention to prevent one of the other outcomes listed in the above definition. These should also be considered serious. Examples of such events are invasive or malignant cancers, intensive treatment in an emergency room or at home for allergic bronchospasm, blood dyscrasias or convulsions that do not result in hospitalisation.

### 8.1.3. **Solicited adverse events**

The following local (injection-site) AEs will be solicited:

**Table 14      Solicited local adverse events**

All age groups
Pain at injection site
Redness at injection site
Swelling at injection site

The following general AEs will be solicited:

**Table 15      Solicited general adverse events**

Drowsiness
Fever
Irritability/Fussiness
Loss of appetite

Note: Temperature (by axillary route preferred) will be recorded in the evening. Should additional temperature measurements be performed at other times of day, the highest temperature will be recorded in the eCRF.

### 8.1.4. **Clinical laboratory parameters and other abnormal assessments qualifying as adverse events or serious adverse events**

In absence of diagnosis, abnormal laboratory findings (e.g. clinical chemistry, haematology, urinalysis) or other abnormal assessments that are judged by the investigator to be clinically significant will be recorded as AEs or SAEs if they meet the definition of an AE or SAE (refer to Sections 8.1.1 and 8.1.2). Clinically significant abnormal laboratory findings or other abnormal assessments that are present at baseline and significantly worsen following the start of the study will also be reported as AEs or SAEs. However, clinically significant abnormal laboratory findings or other abnormal assessments that are present or detected at the start of the study and do not worsen, will not be reported as AEs or SAEs.

The investigator will exercise his or her medical and scientific judgement in deciding whether an abnormal laboratory finding or other abnormal assessment is clinically significant.

### 8.1.5. **Other adverse events**

#### 8.1.5.1. **Potential immune-mediated diseases**

Potential immune-mediated diseases (pIMDs) are a subset of AEs that include autoimmune diseases and other inflammatory and/or neurologic disorders of interest which may or may not have an autoimmune aetiology. AEs that need to be recorded and reported as pIMDs include those listed in [Table 16](#).

However, the investigator will exercise his/her medical and scientific judgement in deciding whether other diseases have an autoimmune origin (i.e. pathophysiology

**CONFIDENTIAL**

116938 (FLU Q-PAN H5N1=AS03-023)

Protocol Amendment 2 Final

involving systemic or organ-specific pathogenic autoantibodies) and should also be recorded as a pIMD.

**Table 16 List of potential immune-mediated diseases**

Neuroinflammatory disorders	Musculoskeletal disorders	Skin disorders

 
• Cranial nerve disorders, including paralyses/paresis (e.g. Bell's palsy)
 
• Optic neuritis
 
• Multiple sclerosis
 
• Transverse myelitis
 
• Guillain-Barré syndrome, including Miller Fisher syndrome and other variants
 
• Acute disseminated encephalomyelitis, including site specific variants: e.g. non-infectious encephalitis, encephalomyelitis, myelitis, myeloradiculoneuritis
 
• Myasthenia gravis, including Lambert-Eaton myasthenic syndrome
 
• Immune-mediated peripheral neuropathies and plexopathies, (including chronic inflammatory demyelinating polyneuropathy, multifocal motor neuropathy and polyneuropathies associated with monoclonal gammopathy).
 
• Narcolepsy
 
	
 
• Systemic lupus erythematosus and associated conditions
 
• Systemic sclerosis (Systemic sclerosis), including diffuse systemic form and CREST syndrome
 
• Idiopathic inflammatory myopathies, including dermatomyositis
 
• Polymyositis
 
• Antisynthetase syndrome
 
• Rheumatoid arthritis, and associated conditions including juvenile chronic arthritis and Still's disease
 
• Polymyalgia rheumatica
 
• Spondyloarthritis, including ankylosing spondylitis, reactive arthritis (Reiter's Syndrome) and undifferentiated spondyloarthritis
 
• Psoriatic arthropathy
 
• Relapsing polychondritis
 
• Mixed connective tissue disorder
 
	
 
• Psoriasis
 
• Vitiligo
 
• Erythema nodosum
 
• Autoimmune bullous skin diseases (including pemphigus, pemphigoid and dermatitis herpetiformis)
 
• Alopecia areata
 
• Lichen planus
 
• Sweet's syndrome
 
• Localised Scleroderma (Morphea)
 

Vasculitides	Blood disorders	Others

 
• Large vessels vasculitis including: giant cell arteritis such as Takayasu's arteritis and temporal arteritis.
 
• Medium sized and/or small vessels vasculitis including: polyarteritis nodosa, Kawasaki's disease, microscopic polyangiitis, Wegener's granulomatosis, Churg-Strauss syndrome (allergic granulomatous angiitis), Buerger's disease (thromboangiitis obliterans), necrotizing vasculitis and anti-neutrophil cytoplasmic antibody (ANCA) positive vasculitis (type unspecified), Henoch-Schonlein purpura, Behcet's syndrome, leukocytoclastic vasculitis.
 
	
 
• Autoimmune hemolytic anemia
 
• Autoimmune thrombocytopenia
 
• Antiphospholipid syndrome
 
• Pernicious anemia
 
• Autoimmune aplastic anaemia
 
• Autoimmune neutropenia
 
• Autoimmune pancytopenia
 
	
 
• Autoimmune glomerulonephritis (including IgA nephropathy, glomerulonephritis rapidly progressive, membranous glomerulonephritis, membranoproliferative glomerulonephritis, and mesangioproliferative glomerulonephritis)
 
• Ocular autoimmune diseases (including autoimmune uveitis and autoimmune retinopathy)
 
• Autoimmune myocarditis/cardiomyopathy
 
• Sarcoidosis
 
• Stevens-Johnson syndrome
 
• Sjögren's syndrome
 
• Idiopathic pulmonary fibrosis
 
• Goodpasture syndrome
 
• Raynaud's phenomenon
 

Liver disorders	Gastrointestinal disorders	Endocrine disorders

 
• Autoimmune hepatitis
 
• Primary biliary cirrhosis
 
• Primary sclerosing cholangitis
 
• Autoimmune cholangitis
 
	
 
• Inflammatory Bowel disease, including Crohn's disease, ulcerative colitis, microscopic colitis, ulcerative proctitis
 
• Celiac disease
 
• Autoimmune pancreatitis
 
	
 
• Autoimmune thyroiditis (including Hashimoto thyroiditis)
 
• Grave's or Basedow's disease
 
• Diabetes mellitus type I
 
• Addison's disease
 
• Polyglandular autoimmune syndrome
 
• Autoimmune hypophysitis
 

When there is enough evidence to make any of the above diagnoses, the AE must be reported as a pIMD, *as per Section 8.3.3*. Symptoms, signs or conditions which might (or might not) represent the above diagnoses, should be recorded and reported as AEs but not as pIMDs until the final or definitive diagnosis has been determined, and alternative diagnoses have been eliminated or shown to be less likely.

In order to facilitate the documentation of pIMDs in the eCRF, a pIMD standard questionnaire and a list of preferred terms (PTs) and PT codes corresponding to the above diagnoses will be available to investigators at study start.

#### **8.1.5.2. CHMP-defined adverse events of special interest (AESIs)**

AESIs are a subset of AEs that are defined in the Committee for Medicinal Products for Human Use (CHMP) Risk Management Plan for Pandemic Vaccines for safety monitoring.

Reports of AESIs will be identified by searching the clinical database using MedDRA Preferred Terms (PTs) or Standardized MedDRA Queries (SMQs) as recommended by CHMP. SMQs are groupings of MedDRA terms, usually at the PT level, that relate to a defined medical condition or event of interest and are intended to aid in the identification of case reports of these events. AESIs include the events listed below and the MedDRA PT or SMQ used to identify reports of these events is provided in parentheses:

- Anaphylaxis (narrow SMQs “Anaphylactic reaction” and “Angioedema”)
- Bell’s palsy (MedDRA PT “VIIth nerve palsy”)
- Convulsion (narrow SMQ “Convulsions”)
- Demyelination (narrow SMQ “Demyelination”)
- Encephalitis (narrow SMQ “Non-infectious encephalitis”)
- Guillain-Barré syndrome (narrow SMQ “Guillain-Barré syndrome”)
- Neuritis (MedDRA PT “Neuritis”)
- Vasculitis (narrow SMQ “Vasculitis”)

With the exception of anaphylaxis and convulsion, all AESIs and associated preferred terms are also considered to be pIMDs (Section 8.1.5.1) and will be reported as such (Section 8.3.3).

### **8.2. Detecting and recording adverse events/SAEs**

Types of adverse events to be collected during this study are as follows.

- Solicited local and general adverse events ([Table 14](#) and [Table 15](#)), and
- Unsolicited adverse events, including (but not limited to) those which:
  - are medically attended (“MAEs,” see [glossary of terms](#)),
  - are potential immune mediated diseases (“pIMDs,” [Table 16](#)), and/or

- meet the definition of a serious adverse event (“SAEs,” see [glossary of terms](#)).

Methods used to detect and record both solicited and unsolicited adverse events include:

- Diary cards,
- Scripted telephone interviews,
- Interactions with site personnel at study visits, *and*
- Searching database for pIMDs as per list in [Table 16](#) (see Section [8.1.5.1](#)) and for AESIs according to defined PTs and SQMs (see Section [8.1.5.2](#)).

### **8.2.1. Time periods for detecting and recording adverse events/SAEs**

All solicited and unsolicited AEs must be recorded into the appropriate section of the eCRF, irrespective of intensity or whether or not they are considered vaccination-related.

Solicited AEs must be recorded for 7 days, i.e. on the day of each study vaccination and for the next 6 days after (i.e., Day 0 to Day 6 (dose 1); Day 21 to Day 27 (dose 2); Day 385 to Day 392 (booster dose)).

The time period for collecting and recording information about occurrences of AEs leading to withdrawal from the study, MAEs, pIMDs and SAEs will begin with the first study vaccine dose and will end when the subject is discharged from the study. See Section [8.3](#) for special instructions on reporting of pIMDs and SAEs.

In addition to the above-mentioned reporting requirements and in order to fulfil international reporting obligations, SAEs that are related to study participation (i.e. protocol-mandated procedures, invasive tests, a change from existing therapy) or are related to a concurrent GSK medication/vaccine will be collected and recorded from the time the subject consents to participate in the study until she/he is discharged from the study.

Occurrences of all other unsolicited AEs must be recorded from the time of the first receipt of study vaccine through completion of the Day 42 visit (Day 0 to Day 42) as well as on day of booster dose (Day 385 and 30 days after booster to Day 415) or until the subject is withdrawn or lost to follow-up.

The clinical database will be searched for events corresponding to AESIs; this will include any AEs reported from Day 0 to Day 42 or within 30 days post-booster, as well as any MAEs, SAEs or pIMDs reported during the entire study period.

[Table 17](#) provides an overview of the protocol-required reporting periods for collecting safety information.

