Sub-cohort:	A group of subjects for whom specific study procedures are planned as compared to other subjects.
Subject:	Term used throughout the protocol to denote an individual who has been contacted in order to participate or participates in the clinical study, either as a recipient of the vaccine(s)/product(s) or as a control.
Treatment:	Term used throughout the clinical study to denote a set of investigational product(s) or marketed product(s) or placebo intended to be administered to a subject, identified by a unique number, according to the study randomisation or treatment allocation.
Unsolicited adverse event:	Any AE reported in addition to those solicited during the clinical study. Also any 'solicited' symptom with onset outside the specified period of follow-up for solicited symptoms will be reported as an unsolicited adverse event.
Vaccine response rate for microneutralization titers:	The incidence rate of subjects with at least a 4-fold increase in post vaccination reciprocal titer relative to pre-vaccination titers). Titers less than the cut-off titer are considered to be one-half the cut-off titer.

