Note: The double-line border following Day 42 indicates analyses will be performed on all data obtained up to this time point; Pre-Vacc: Pre-vaccination. Post-Vacc: Post-vaccination.. TC = telephone contact. ● is used to indicate a study procedure that requires documentation in the individual eCRF.

○ is used to indicate a study procedure that does not require documentation in the individual eCRF

\* If any, it has to be recorded in medical history (prior first vaccination) or in AE/SAE.

1. Influenza vaccination history will include all previous seasonal influenza vaccination(s)]
2. Diary cards used to capture both solicited (for 7 days following each dose) and unsolicited events (for 21 days after doses 1 and 2; for 30 days after booster dose) are provided at the time of each vaccination and collected at the next visit after each vaccination.
3. Recording of intensity and duration of solicited local symptoms and of occurrence, intensity, duration, and relationship of each solicited general AE and unsolicited AE;
4. Recording of intensity, duration and relationship to vaccination of each event reported. Reported events will be searched for AESIs.

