**Table 7 Intervals between study visits**

Interval (by visit number)	Interval (by visit name)	Optimal length of interval 	Allowed interval
Visit 1 → Visit 2	Visit Day 0 → Visit Day 21	21 days	18 - 25 days 
Visit 1 → Visit 3	Visit Day 0 → Visit Day 42	42 days	38 - 46 days 
Visit 1 → Visit 4 (TC1)	Visit Day 0 → TC Day 90	90 days	80 - 100 days
Visit 1 → Visit 5 (TC2)	Visit Day 0 → TC Day 240	240 days	220 - 260 days
Visit 1 → Visit 6	Visit Day 0 → Visit Day 385	385 days	375 - 395 days 
Visit 6 → Visit 7	Visit Day 385 → Visit Day 392	7 days	6 - 10 days 
Visit 6 → Visit 8 (TC3)	Visit Day 385 → Visit Day 415	30 days	30 - 45 days

Whenever possible the investigator should arrange study visits within this interval.

 Subjects will not be eligible for inclusion in the ATP cohort for immunogenicity analysis for that specific interval if vaccine administration and blood collections are outside these intervals.

TC = telephone contact

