7.1.3. Reactogenicity and safety

Incidence rates of AEs will be calculated as the number of subjects who experience the event, divided by the number of subjects in the safety analysis cohort (the TVC).

Handling of missing safety data:

- **Solicited AEs:** For a given subject and the analysis of solicited AEs within 7 days post-vaccination (Days 0 through 6), missing or non-evaluable measurements will not be replaced.
 - The analysis of the solicited AEs will include only vaccinated subjects and doses with documented safety data (i.e., symptom screen/sheet completed, including the response ‘Yes’ or ‘No’ to the solicited symptom page).
 - Subjects who answered “Yes” in the solicited symptom page, but had all symptoms missing are considered as having no solicited symptoms.
 - Subjects who answered ‘Yes’ to the presence of a specific symptom but partially recorded the daily measurement (e.g. intensity missing for Day 3) over the considered solicited period will be included in the summaries and classified according to their maximum observed daily recording over the solicited period.
 - Subjects who answered ‘Yes’ to the presence of a specific symptom but recorded no daily measurement over the considered solicited period will not be counted in the summary of symptoms by grade/category but will be part of the summary corresponding to the ‘All’ category for that symptom.
- **Unsolicited AEs:** For the analysis of unsolicited AEs/MAEs/SAEs/pIMDs/AESIs, all vaccinated subjects will be considered and subjects who did not report an event will be considered as subjects without an event.
- **Concomitant medication and vaccination:** For the analysis of concomitant medications and vaccinations, all vaccinated subjects will be considered and subjects who did not report an event will be considered as subjects without an event.

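### Section 8.2.1 lists an 8-day solicited window for the booster against its own 7-day rule, and a compliant Visit 7 on day 6 collects the booster card before the last evening

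*Protocol*

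**What the plan says.** Protocol section 8.2.1 gives a rule and then the dates. The rule is "Solicited AEs must be recorded for 7 days, i.e. on the day of each study vaccination and for the next 6 days after". The dates that follow in the same sentence are "Day 0 to Day 6 (dose 1); Day 21 to Day 27 (dose 2); Day 385 to Day 392 (booster dose".

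Elsewhere the window is 7 days for every dose: the booster safety objective (section 2.2), the parent-recording row of Table 6 (Day 0 to 6, marked at Visits 1, 2 and 6), section 5.6.12, and the endpoints in section 10.2. SAP Amendment 2, section 7.1.3, defines "the analysis of solicited AEs within 7 days post-vaccination (Days 0 through 6", and its section 8.1.3 applies Day 0-6 after each vaccination. Table 17 has D0-D6 and D21-D27 columns for the priming doses. It has no matching range for the booster, whose only solicited entry stands under D392.

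The protocol glossary, under unsolicited adverse event, says: "Also any 'solicited' symptom with onset outside the specified period of follow-up for solicited symptoms will be reported as an unsolicited adverse event".

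On the card, Table 6 footnote 2 says that diary cards "are provided at the time of each vaccination and collected at the next visit after each vaccination". For the booster the next visit is Visit 7. The Table 7 row "Visit Day 385 → Visit Day 392" gives 7 days as optimal and 6 to 10 days as allowed. The note to Table 15 says: "Temperature (by axillary route preferred) will be recorded in the evening". It adds that if other readings are taken, the highest is recorded.

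**The concern.** The solicited window decides how an event is classified. With a 7-day window, a fever starting on Day 392 is an unsolicited AE under the glossary. With the range listed in 8.2.1 it is solicited, so the site has no reason to enter it as unsolicited, yet the SAP's solicited analysis ends at Day 6 after vaccination (Day 391). The event could then be missing from both sets of tables. Table 17, which 8.2.1 names as its overview, does not settle the matter, because D392 is the only booster date it shows for solicited events.

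The second matter is separate. A Visit 7 on day 6 is within the allowed interval, but a card handed in during that day cannot yet hold the evening reading. The shortfall would not be visible in the results. SAP section 7.1.3 does not replace missing measurements and grades a partial record by its highest observed value. Under section 7.1.3.1 a child counts in the denominator once any one solicited symptom of that type is documented. A child with six evenings therefore counts the same as one with seven.

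**Working it through.** **Length of each listed window.** The plan's figure is 7 days. The inclusive count is last day − first day + 1, using the ranges in section 8.2.1.

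- Dose 1: 6 − 0 + 1 = 7. Agrees.
- Dose 2: 27 − 21 + 1 = 7. Agrees.
- Booster as listed: 392 − 385 + 1 = 8. Does not agree.
- Booster by the rule: 385 + 6 = 391, and 391 − 385 + 1 = 7. Agrees with doses 1 and 2 and with the SAP's Days 0 to 6.

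**When each card comes back.** The inputs are the allowed intervals in Table 7: Visit 1 to 2, 18–25 days; Visit 1 to 3, 38–46 days; Visit 6 to 7, 6–10 days.

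- Dose 1: 18 to 25 days after the dose.
- Dose 2: 38 − 25 = 13 days at the earliest, 46 − 18 = 28 at the latest.
- Booster: 6 to 10 days.

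Only the booster card can be returned before its 7-day window closes.

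**Evenings on the booster card.** At a daytime visit d days after vaccination, d evenings have passed, counting the evening of vaccination. The card therefore holds min(d, 7) of the 7 readings in the analysed window.

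| Visit 7 on day | Study day | Evenings of the 7-day window |
|---|---|---|
| 6 | 391 | 6 of 7 |
| 7 (optimal) | 392 | 7 of 7 |
| 8 to 10 | 393 to 395 | 7 of 7 |

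An eighth evening (Day 392) would also be missing at the optimal visit. That does not affect the analysed rate, because the SAP stops at Day 6.

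**Size of the day-6 effect.** The documents give no daily fever risk after the booster and no distribution of Visit 7 dates, so both are assumed. With a constant daily risk h of a first fever, incidence over k days is 1 − (1 − h)^k.

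| Assumed h | 6 days | 7 days | Difference |
|---|---|---|---|
| 0.5% | 3.0% | 3.4% | 0.5 points |
| 1% | 5.9% | 6.8% | 0.9 points |
| 2% | 11.4% | 13.2% | 1.8 points |

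Differences are taken before rounding. They apply in full only if every child is seen on day 6 and the whole of the last day is lost. If a share p is seen on day 6, multiply by p. With an assumed p of 20%: 0.2 × 0.5 = 0.1 and 0.2 × 1.8 = 0.36, so about 0.1 to 0.4 points.

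**The case against.** The best answer is that Day 392 is a one-digit slip. The rule stands in the same sentence, Table 6 and section 5.6.12 give parents 7 days, and nothing in the documents shows a card or eCRF with an eighth booster day. Losing a Day 392 onset requires a site to prefer the stray date to the rule. Medically attended and serious events are collected throughout the study in any case. Much of this stands: a slip is the likeliest explanation, and the loss is a possibility and not an expected result. But the range is an instruction to sites about what to record, and Table 17 does not correct it, so it needs changing.

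On the card, one can say that daytime readings on the last day may already be recorded, that site staff speak with the parent at Visit 7, and that Table 6 distributes a card at Visit 7 and lists transcription at Visit 8. The loss can therefore be partial. However, Table 6 marks parent recording of solicited events only at Visits 1, 2 and 6, and nowhere says that the Visit 7 card continues the solicited record.

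A reader might go further and infer that booster solicited events in general are ascertained over 6, 7 or 8 days, so that booster rates are not comparable with doses 1 and 2. The documents do not support that. The SAP analyses Days 0 to 6 after every vaccination, so an eighth day cannot enter the rate, and a Visit 7 on days 7 to 10 covers the full window. Nor is a bias between groups shown: all groups receive the same unadjuvanted booster under the same visit window. The fever rise cited in section 1.2 was seen with adjuvanted doses, and priming and booster safety are separate descriptive objectives.

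**Conclusion.** Two minor points hold. First, section 8.2.1 contradicts itself on the booster window (8 days listed, 7 by rule), and a site following the listed range could leave a Day 392 onset out of both the solicited and the unsolicited tables. Second, a compliant day-6 Visit 7 can cut the last evening from the analysed window.

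The second affects only children seen on exactly day 6, whose number is unknown. The effect on the booster fever rate is at most about 0.5 to 1.8 points under the assumed daily risks, and proportionately less if few children attend that early. The calculation assumes a constant daily risk, a daytime visit and complete loss of the last day, so it is an upper bound for those risks. The co-primary immunogenicity-fever index is untouched: under section 10.6.2.1 it uses temperatures from Days 0 to 2 after doses 1 and 2 only.

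**What to change.** In section 8.2.1, change the booster range to Day 385 to Day 391, and make the booster solicited entry in Table 17 show the same period. A symptom that starts later is then entered as an unsolicited AE, as the glossary already requires. The SAP needs no change. Confirm that the booster diary card and the eCRF carry seven days.

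In section 5.6.12 and Table 6 footnote 2, state that when Visit 7 falls on day 6 the parent writes that evening's solicited entries on the card handed out at Visit 7, and that they are transcribed at the Day 415 contact. Table 6 already provides both that card and that transcription step. Footnote 2 must change as well as 5.6.12, because it now has the card collected at the next visit without exception.

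The cost is short text edits in four places and no new visit or card. The downside is one more item at the Day 415 call for children seen on day 6.
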